6.4.8. Percentage of Time Spent in Standing Position and Other Wearable Device Variables

Positions while wearing the recording device were categorized as follows:

- Lying down
- Sitting
- Standing (including walking)

The percentage of time spent walking was also captured.

To obtain percentage of time spent in standing position and the other wearable device variables, subjects were asked to wear their devices for at least 2 consecutive days within the 5 days before each visit at which device data were to be obtained.

Because of rounding, sums of percentages across positions may exceed 100%.

6.5. Visit Windows

All assessments will be summarized using analysis windows. The term “out of window” will be applied to assessments that are outside an analysis window, regardless of the visit label associated with the assessments in the EDC system.

In this study, analysis windows will be defined separately for visits during the open-label treatment period and the randomized withdrawal treatment period of the study, according to the protocol-specified visit schedule. The nominal day 1 is the date of first dose of the open-label treatment, the other nominal visits during the open-label treatment period will be determined based on the days from the start of open-label dosing. The nominal day 113 is date of first dose of the randomized treatment, the other nominal visits during the randomized withdrawal treatment period will be determined based on the days from the first randomized dose date. Generally, the analysis window will be defined using the middle points between the consecutive visits (Table 3).

For De Novo subjects, both the Baseline/Screening Version and the Since Last Visit Version of the C-SSRS are collected prior to the 1st open-label dose of the study medication. The Baseline/Screening Version of the C-SSRS collected at Screening will be used as the baseline. There will be no specific analysis window for the Since Last Visit Version of the C-SSRS collected at Visit 1/Day 1; the data will be included in the summary unless the Since Last Visit Version of the C-SSRS is collected on the same day as the Baseline/Screening Version of the C-SSRS.

The following visit windows will be used in the summary of clinical data:

Table 3: Analysis Visit Windows

Nominal Period	Start (days)	Stop (days)
Vital signs (BP, HR, RR, and body temperature)		
OL Baseline	Last result prior to first dose in OL Period	
Week 2 (Day 14)	2	20
Week 4 (Day 28)	21	41
Week 8 (Day 56)	42	69
Week 12 (Day 84)	70	97
Week 16 (Day 112)	98	First Dose in RW Period [1]
RW Baseline	Last result prior to First Dose in RW Period [1]	
First Dose Day in RW Period (DD)		
Week 18 (Day 126) (DD+13)	First Dose in RW Period [1]	DD+20
Week 20 (Day 140) (DD+27)	DD+21	DD+34
Week 22 (Day 154) (DD+41)	DD+35	EOS
OHQ (OHSA and OHDS), ████████ C-SSRS, PGI-S, Wearable device provision/collection, Orthostatic standing test		
OL Baseline	Last result prior to first dose in OL Period	
Week 4 (Day 28)	2	41
Week 8 (Day 56)	42	69
Week 12 (Day 84)	70	97
Week 16 (Day 112)	98	First Dose in RW Period [1]
RW Baseline	Last result prior to First Dose in RW Period [1]	
First Dose Day in RW Period (DD)		
Week 18 (Day 126) (DD+13)	First Dose in RW Period [1]	DD+20
Week 20 (Day 140) (DD+27)	DD+21	DD+34

Week 22 (Day 154) (DD+41)	DD+35	EOS
[REDACTED]		
[REDACTED]	[REDACTED]	
[REDACTED]	[REDACTED]	[REDACTED]
[REDACTED]	[REDACTED]	[REDACTED]
[REDACTED]	[REDACTED]	
[REDACTED]		
[REDACTED]	[REDACTED]	[REDACTED]
Safety laboratory test results (chemistry, hematology, and urinalysis)		
OL Baseline	Last result prior to first dose in OL Period	
Week 2 (Day 14)	2	34
Week 8 (Day 56)	35	83
Week 16 (Day 112)	84	First Dose in RW Period [1]
RW Baseline	Last result prior to First Dose in RW Period [1]	
First Dose Day in RW Period (DD)		
Week 22 (Day 154) (DD+41)	First Dose in RW Period [1]	EOS
ECGs		
OL Baseline	Last result prior to first dose in OL Period	
Week 4 Day 28	2	71
Week 16 (Day 112)	72	First Dose in RW Period [1]
RW Baseline	Last result prior to First Dose in RW Period [1]	
First Dose Day in RW Period (DD)		
Week 22 (Day 154) (DD+41)	First Dose in RW Period [1]	EOS

ABPM (collected in OL period only)		
Open-Label Baseline	Last results collected prior to first dose in OL Period	
Week 2 (Day 14)	2	23
Week 8 (Day 56)	24	OL Disposition Date

[1] First dose in RW period: When both a date and time are available for the first dose in the RW period and the assessment of interest, dates and times are used to determine the end of Analysis Week 16 (Day 112) and the beginning of the first applicable analysis week in the RW period, e.g. Analysis Week 18 (Day 126): An assessment is assigned to Analysis Week 16 (Day 112) if its date and time are prior to the date and time of the first dose in the RW period, and it is assigned to the first applicable analysis week in the RW period, e.g. Analysis Week 18 (Day 126) if it is on/after the date and time of the first dose in the RW period.

If only the date of the first dose in the RW period and/or the assessment of interest is available, dates are used to determine the end of Analysis Week 16 (Day 112) and the beginning of the first applicable analysis week in the RW period, e.g., Analysis Week 18 (Day 126): In this case, an assessment with a date prior to or on the date of first dose in the RW period is assigned to Analysis Week 16 (Day 112), and it is assigned to Week 18 (Day 126) if it is after the date of first dose in the RW period. In other words, if a subject took their first RW dose on the same day as their Visit 6 Day 113 visit, it is assumed that all assessments were done prior to the subject taking that first RW dose.

Nominal Period	Start (days)	Stop (days)
Vital signs (BP, HR, RR, and body temperature), incidence of Falls and ABPM position Diaries		
Open-Label Baseline		
Week 2 (Day 14)	2	20
Week 4 (Day 28)	21	41
Week 8 (Day 56)	42	69
Week 12 (Day 84)	70	97
Week 16 (Day 112)	98	Last day prior to randomization
RW Baseline First dose date in RW (DD)		
Week 18 (DD+13)	DD	DD+20
Week 20 (RD+27)	DD+21	DD+34
Week 22 (RD+41)	DD+35	EOT
OHQ (OHSa and OHDAS), ██████████, C-SSRS, PGI-S, Wearable device provision/collection, Orthostatic standing test		
Open-Label Baseline		
Week 4 (Day 28)	2	41
Week 8 (Day 56)	42	69
Week 12 (Day 84)	70	97
Week 16 (Day 112)	98	Last day prior to randomization
Randomized Withdrawal Baseline First dose date in RW (DD)		
Week 18 (DD+13)	DD	DD+20
Week 20 (RD+27)	DD+21	DD+34
Week 22 (RD+41)	DD+35	EOT
██		
████████████████████		
████████████████████	█	█
████████████████████	█	██
████████████████████ ████████████████████		
████████████████████	█	█
Safety laboratory test (chemistry, hematology, and urinalysis)		

Nominal Period	Start (days)	Stop (days)
Vital signs (BP, HR, RR, and body temperature), incidence of Falls and ABPM position Diaries		
Open-Label Baseline		
Week 2 (Day 14)	2	20
Week 4 (Day 28)	21	41
Week 8 (Day 56)	42	69
Week 12 (Day 84)	70	97
Week 16 (Day 112)	98	Last day prior to randomization
RW Baseline First dose date in RW (DD)		
Week 18 (DD+13)	DD	DD+20
Week 20 (RD+27)	DD+21	DD+34
Week 22 (RD+41)	DD+35	EOT
OHQ (OHSa and OHDAS), ██████s, C-SSRS, PGI-S, Wearable device provision/collection, Orthostatic standing test		
Open-Label Baseline		
Week 4 (Day 28)	2	41
Week 8 (Day 56)	42	69
Week 12 (Day 84)	70	97
Week 16 (Day 112)	98	Last day prior to randomization
Randomized Withdrawal Baseline First dose date in RW (DD)		
Week 18 (DD+13)	DD	DD+20
Week 20 (RD+27)	DD+21	DD+34
Week 22 (RD+41)	DD+35	EOT
██		
████████████████		
████████████████	█	█
████████████████	█	█
████████████████	█	██
████████████████ ████████████████		
████████████████	█	█

6.5.1. Multiple Assessments

In general, if multiple valid observations exist at a visit or collection time point, the record to be included in the summary and analyses will be chosen based on the following:

- The record closest to the nominal time

If 2 records are equidistant or distance cannot be determined:

- The later record

If 2 or more records with same date/time:

- Average (generally applies to assessments done in triplicate)

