6.4.10.7. Vital Signs

The HR, SBP and DBP, RR, and body temperature will be recorded according to the Schedule of Study Procedures ([Table 1](#)). The vital sign measurements (BP and HR) should be performed after the subject has rested sufficiently as determined by the appropriate staff.

Subject position, measurement device, and arm (left vs. right) should be kept consistent throughout the study. Blood pressure will be measured using a calibrated manual or automatic BP device.

Heart rate will be recorded by palpation of the radial pulse over at least a 30-second period or by the automated BP device.

The BP and HR collected at 10 minutes supine and seated from the orthostatic standing test can be used for safety vital sign assessment.

Body temperature will be measured and reported in degrees Celsius. The method used to collect temperature can be either oral or tympanic but should be consistent throughout the subject's participation.

Any vital sign outside the normal range may be repeated at the discretion of the Investigator. Collection of additional vital sign measurements for routine safety monitoring at additional time points or study days may be performed at the discretion of the Investigator, or upon request by the sponsor.

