6.4.10.12. Unscheduled Visit

All sites are allowed at Investigator discretion to conduct either in clinic or remote unscheduled visit(s) for subject safety or unexpected subject medical needs outside of the regular visit schedule. In this case, unscheduled visits are not considered protocol deviations and the Investigator is not required to obtain pre-approval from the Sponsor. Data collected during these visits may include any protocol-specified assessments which will be captured in the clinical database.

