8.6. Safety Analyses

Safety data, including C-SSRS, will be descriptively summarized separately for OL phase and double-blind randomized withdrawal phase.

The OL phase data will be summarized for all subjects and by enrollment group (De Novo Group or 0169 Completers Group), and the double-blind randomized withdrawal phase data will be summarized by treatment group according to treatment subjects received. Quantitative data collected at unscheduled times will be listed but will not be included in summaries. Categorical data collected at unscheduled times (e.g., ECG finding categories) will not be included in summaries by time point but will be included in summaries of findings during the entire treatment period.

Safety analyses will be performed using the safety analysis set. Unless specified otherwise, there will be no imputation of missing data in safety summaries. Subjects without post baseline measurement (e.g. ECG or vital signs) for a given time point will be excluded from the summary statistic (e.g., denominator of the summary statistic) for that time point.

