6. CONSIDERATIONS FOR DATA ANALYSES AND HANDLING

All data from both scheduled and unscheduled visits will be presented in data listings.

However, unless noted otherwise, only data from visits (scheduled or unscheduled) that fall within analysis windows will be included in summaries, statistical analyses, and calculation of derived variables. [REDACTED] 5.

Analyses and tabulations will be prepared [REDACTED]

Summary tables and listings will be prepared according to ICH Guideline E3 and will include a “footer” providing explanatory notes.

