9.5. Vital Signs and Weight

Weight and vital signs (HR and systolic and diastolic BP) and their changes from baseline at postbaseline visits will be summarized. (Following the start of the open-label treatment period, weight is collected at the beginning and end of the randomized withdrawal treatment period and at the 10-day follow-up visit.) At visits when orthostatic standing test results are collected, the vital signs (BP and HR) collected after 10 minutes supine and 10 minutes seated from the orthostatic standing test will be used for these summaries. Therefore, the BP and HR summaries for these visits will include body position (supine and seated). At Visit 2 (Day 15), which does not include an orthostatic standing test, the position in which BP and HR were collected is not recorded. Visit 2 measurements will be assumed to have been collected while the subjects were seated.

The counts and percentages of subjects with vital signs in the ranges shown in [Table 9](#) will be presented in an extreme values summary. Extreme values will be flagged in the listing.

Table 9: Vital Signs Extreme Value Thresholds

Heart Rate (bpm)	Systolic Blood Pressure (mmHg)	Diastolic Blood Pressure (mmHg)
< 40	< 85	< 45
> 110	> 160	> 100

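### By default the Table 9 and Table 10 threshold counts use one record per analysis window, so most extreme values found at unscheduled visits on another day would not be counted

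*SAP*

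**What the plan says.** **Which data enter.** SAP 6 states, subject to any exception written elsewhere, that "only data from visits (scheduled or unscheduled) that fall within analysis windows will be included in summaries, statistical analyses, and calculation of derived variables". SAP 6.5 adds: "All assessments will be summarized using analysis windows".

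**Which record is used.** SAP 6.5.1, worded as a general rule for a visit with several valid observations, says that "the record to be included in the summary and analyses will be chosen based on the following". First in its order of choice comes "The record closest to the nominal time". If two records are equally distant, the later one is used. Records with an identical date and time are averaged.

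**Which tables depend on it.** In SAP 9.5 the counts of subjects beyond the Table 9 limits (SBP below 85 or above 160 mmHg, DBP below 45 or above 100 mmHg, heart rate below 40 or above 110 bpm) "will be presented in an extreme values summary. Extreme values will be flagged in the listing". The section does not say which record is counted, or whether the table is by visit or by period. At visits with an orthostatic standing test it takes BP and heart rate from the 10-minute supine and seated readings. Day 15 has no standing test and body position is not recorded there. SAP 9.6 presents Table 10 by visit.

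**Where extra readings come from.** Protocol 6.4.10.7: "Any vital sign outside the normal range may be repeated at the discretion of the Investigator". Protocol 6.4.10.12 lets sites hold "unscheduled visit(s) for subject safety or unexpected subject medical needs outside of the regular visit schedule", and the results go into the trial database.

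**What the protocol says about them.** Protocol 8.6: "Quantitative data collected at unscheduled times will be listed but will not be included in summaries". It then keeps unscheduled categorical findings, with ECG categories as the example, in summaries covering the whole treatment period. SAP 11.2 lists three changes from the protocol; none concerns unscheduled data.

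**The concern.** Choosing the record nearest the nominal day suits a by-visit mean, because it gives one comparable value per subject. A threshold table has a different purpose: it should show how many subjects ever went beyond a limit. Unscheduled visits exist for subject safety, and repeats are allowed because a value was out of range, so the readings that lose the selection are not a random subset.

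Blood pressure matters here. Protocol 1.4 names increased BP as an important potential risk, and Protocol 7.1.4 makes supine hypertension an adverse event of special interest. Ambulatory monitoring is collected in the open-label period only and is summarized as averages. Table 9 is therefore the only visible count by arm of high BP readings in the randomized period. If it runs low, readers of the report will see fewer subjects beyond the limits than the database holds.

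**Working it through.** The documents give no figure for this, so there is none to reproduce. The check applies SAP 6.5.1 to the Table 3 vital-sign windows.

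**Inputs.** Windows and nominal days are from SAP Table 3. The scheduled visit may fall up to 3 days either side of nominal (protocol schedule). Assumptions: one scheduled reading per window; one unscheduled reading on any other day in that window; all days equally likely. Weeks 16 and 22 end at an event, so their last day is assumed. DD is the first randomized dose day.

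**Formula.** Let the scheduled visit be d days from nominal (d = -3 to +3) and the unscheduled reading u days from nominal. The unscheduled reading is selected if |u| < |d|, or if |u| = |d| and it is later. The number of selectable days is 0 for d = 0; 1 for +1; 2 for -1; 3 for +2; 4 for -2; 5 for +3; 6 for -3. The sum is 21. A window of L days has 7(L - 1) pairings, so

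share excluded = 1 - 21 / [7(L - 1)] = 1 - 3 / (L - 1).

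| Window | Days | L | Excluded |
|---|---|---|---|
| Week 2 | 2 to 20 | 19 | 1 - 3/18 = 83% |
| Week 4 | 21 to 41 | 21 | 1 - 3/20 = 85% |
| Weeks 8 and 12 | 42 to 69; 70 to 97 | 28 | 1 - 3/27 = 89% |
| Week 16 | 98 to 115 (end assumed) | 18 | 1 - 3/17 = 82% |
| Week 18 | DD to DD+20 | 21 | 1 - 3/20 = 85% |
| Week 20 | DD+21 to DD+34 | 14 | 1 - 3/13 = 77% |
| Week 22 | DD+35 to DD+44 (end assumed) | 10 | 1 - 3/9 = 67% |
| Week 22 | DD+35 to DD+55 (end assumed) | 21 | 1 - 3/20 = 85% |

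If the scheduled visit is on its nominal day (d = 0), no other day can be nearer and 100% are excluded. ECG windows are wider. For the Week 4 ECG window (Days 2 to 71, L = 70) the same formula gives 1 - 3/69 = 96%.

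**Worked cases** (illustrative SBP values, 6.5.1 alone):
- Week 18, scheduled DD+13 = 150, unscheduled DD+7 = 190: 150 is used and the subject is not counted.
- Week 18, scheduled DD+16 = 150, unscheduled DD+12 = 190: 190 is used and the subject is counted.
- Day 15, first reading 190, later same-day repeat 150: 150 is used and the high value is lost.
- Day 15, first reading 150, later same-day repeat 190: 190 is used and counted.

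The same-day cases apply clearly only at Day 15. At the standing-test visits SAP 9.5 fixes the 10-minute readings, so a repeat taken outside the test has no stated route to displace them. Day 15 lies in the open-label period, so this mechanism does not touch the randomized comparison.

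**The two documents side by side.** SAP 6 admits unscheduled quantitative data that fall in a window; Protocol 8.6 keeps them out of summaries. Protocol 8.6 admits unscheduled categorical data to whole-period summaries; the SAP has no such provision. Neither says whether a threshold category built from a reading is quantitative or categorical.

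**The case against.** The strongest reply is that this is an inference from default text. SAP 6.5.1 calls itself a general rule and SAP 9.5 does not state the record basis for Table 9, so the programmer may intend to use every reading. That is fair as far as it goes. But no exception is written, Table 10 is expressly by visit, and a programmer following the text would use one record.

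A second reply also has force: nothing disappears. All readings are listed and extremes are flagged. Subjects with QTcF of at least 500 msec, or a rise above 60 msec, have their own listing. Clinically significant abnormal vital signs must be reported as adverse events (Protocol 7.2), supine hypertension is queried at each visit, and the event summaries use dates, not visit windows. These safeguards stand. They depend on investigator reporting, however, and a listing gives no rate by arm.

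A reader might go further than the documents allow in several ways:
- **Every extreme is dropped.** Not so: a nearer unscheduled reading or a higher later repeat at Day 15 is kept.
- **Repeats remove a calculable fraction of high counts.** This would need a reading-to-reading SD and a repeat policy. The documents give no SD, and repeats are discretionary for any out-of-range value, not only those above 160 mmHg.
- **Ignoring the 5-minute readings is part of the fault.** The 10-minute reading is a prespecified time point that the protocol itself names for safety vital signs. It does not result from SAP 6.5.1.
- **A row at 180/110 mmHg would show how many met the stopping rule.** That rule needs elevation sustained for at least 4 hours, which single readings cannot show.
- **Laboratory shift tables suffer likewise.** No loss has been shown there.

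**Conclusion.** The point holds in this limited form. As written, the plan leaves most extreme values found at unscheduled visits on another day out of Tables 9 and 10, and some high first readings at Day 15. The share passed over is about 67% to 89% of day pairings in the vital-sign windows. It rests on equal weighting of days, one scheduled and one unscheduled reading per window, and assumed ends for Weeks 16 and 22.

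This is a share of readings, not of subjects. The documents do not say how many unscheduled readings to expect, so the number of uncounted subjects cannot be given. The direction is clear: relative to a count of subjects who ever exceeded a limit, the counts are likely too low. How the comparison between arms moves depends on which arm has more unscheduled readings. Separately, SAP 6 and Protocol 8.6 disagree and the difference is unrecorded, which needs settling whatever the size of the loss. The efficacy analyses are not affected.

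**What to change.** 1. In SAP 6.5.1, state that record selection applies to by-visit summaries.
2. In SAP 9.5 and 9.6, add to Tables 9 and 10 a count of each subject once per treatment period. Base it on the worst post-baseline value among all valid scheduled, repeat and unscheduled records. For low limits, worst means lowest. Show BP by body position where recorded, with a row for position not recorded.
3. Keep the by-visit counts beside it, and say in SAP 9.5 whether Table 9 is by visit.
4. Reconcile SAP 6 with Protocol 8.6, including how threshold categories are classed, and record the change in SAP 11.2.

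The cost is some SAP wording and one added block of programming for two tables, from data already captured. The drawback is that subjects with more readings have more chances to exceed a limit, which is why the by-visit counts should stay.

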- l. The vital sign measurements should be performed after the subject has rested sufficiently as determined by the appropriate site staff. The BP and HR collected at 10 minutes supine and seated from the orthostatic standing test can be used for safety vital signs assessment. Vitals can be performed as part of the mandated procedures, if needed.
- m. A full physical examination at the Screening visit will be performed (for de novo subjects only). Subsequent physical examinations, per discretion of the Investigator, can be abbreviated and symptomatic.
- n. ECGs are done in triplicate after the subject has been resting for at least 5 minutes in a seated or supine position before the first reading, with each replicate separated by at least 1 minute. The total time to conduct ECGs ideally would not exceed 15 minutes
- o. In women of childbearing potential only. First, urine beta human chorionic gonadotropin (bHCG) test will be performed and if positive, confirmation with serum bHCG test is required. The pregnancy test must be confirmed negative for a subject to be eligible for this study.
- p. Blood samples will be collected for TD-9855 PK on the days specified. All PK sampling times will be accurately recorded by collection date, hour, and minute. Study medication dosing time on the day before each PK collection and on the day of each PK collection will be accurately recorded by dosing date, hour, and minute by the study staff using time recorded in Dosing Diary by Subjects.

SCHEDULE OF STUDY PROCEDURES (CONTINUED)

- q. Blood samples for pharmacodynamic markers (norepinephrine (NE) and dihydroxyphenylglycol (DHPG)), will be collected after the subject has been seated for 30 minutes. Blood sample for NE will be collected at screening (for De Novo Group subjects only) while samples for both NE and DHPG will be collected on Day 1 and Day 57. Note that all pharmacodynamic marker samples should be collected at approximately (± 1 hour) the same time of day on Day 1 and Day 57 so that time-matched analysis can be performed.

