6.4.10.8. Electrocardiograms

The 12-lead ECGs will be recorded in triplicate and separated by at least 1 minute for each replicate, according to the Schedule of Study Procedures ([Table 1](#)), after the subject has been resting at least 5 minutes in the seated or supine position before the first reading. The total time to conduct ECGs ideally would not exceed 15 minutes. Actual time of the assessment must be recorded for each iteration. The corrected QT interval using the Fridericia's formula (QTcF) will be used. The ECGs should be reviewed on the visit day to allow for any appropriate action, if required.

6.4.10.9. 24-hour Ambulatory Blood Pressure Monitoring

Ambulatory blood pressure monitoring (ABPM) equipment will be provided to the subject during the screening visit for De Novo Group subjects, and on V1 for 0169 Completers Group subjects. Beginning approximately 72 to 24-hours before a subject returns to the scheduled clinic visits that require the procedure, subjects will put on the 24-hour blood pressure monitoring equipment and initiate the recording. Once the 24-hour session is complete, subjects will remove and return the equipment to the research center during the next visit. During each 24-hour session, the BP monitoring device will be programmed to automatically measure BP every 2 hours beginning at the top of the hour. During each 24-hour session, subjects will log their posture at the time of each BP measurement in the provided ABPM Position Diary ([Appendix 4](#)). More details regarding the ambulatory monitoring will be provided in a separate manual. ABPM will be performed as specified in the Schedule of Study Procedures ([Table 1](#)).

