8.6.6. Electrocardiogram Data

The QTcF, PR interval, QT interval, QRS duration, and HR from standard digital ECGs will be summarized in terms of observed values, changes from baseline, and counts and percentages within appropriately defined categories.

Table 3: Electrocardiogram Test Outlier Thresholds

Heart Rate (bpm)	Heart Rate Change From Baseline (bpm)	PR Interval (msec)	PR Percentage Change From Baseline (%)	QRS Interval (msec)	QT _c F (msec)	QT _c F Change From Baseline (msec)
>120	≥20	≥ 200	≥ 15	≥ 120	Males:	≤ 30
>130	≥30	≥ 220	≥ 25		< 430	>30, ≤ 60
					≥ 430	> 60
					≥ 450	
					≥ 470	
					≥ 480	
					≥ 500	
					Females:	
					< 450	
					≥ 450	
					≥ 470	
					≥ 480	
					≥ 500	

In addition, QT_cF (msec) will also be summarized by the following categories: Normal (males <430, females <450), Borderline (males [≥430, <450], females [≥450, <470]), and Prolonged (males ≥450, females ≥470).

All recorded ECG interval values and ECG assessments will be presented in a by-subject listing. A separate listing of subjects with extreme values or changes, as specified in the SAP (e.g., values of QT_cF ≥450 msec if male or ≥470 msec if female, QT_cF increases from baseline >60 msec) will be provided.

Treatment-emergent ECG abnormalities are defined as those not present at baseline, or those that worsened after treatment, e.g., borderline at baseline but were prolonged after treatment.

When multiple values exist for the same nominal time point (e.g., triplicate reading), the average of the readings taken for ECG parameters will be used in the data analysis, including the outlier analysis stated below.

Cumulative distribution plots will be provided for maximum change in QT_cF by day.

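### SAP 6.5.1 says triplicates are averaged but triggers averaging only on an identical date and time, which protocol-compliant ECG replicates do not have

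*SAP*

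**What the plan says.** **SAP 6.5.1 (Multiple Assessments)** gives a general rule for choosing the record to analyse when a visit has several valid ones, in three steps:

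1. "The record closest to the nominal time".
2. "If 2 records are equidistant or distance cannot be determined", the later record.
3. "If 2 or more records with same date/time", then "Average (generally applies to assessments done in triplicate").

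**Protocol 6.4.10.8 (Electrocardiograms)** states: "The 12-lead ECGs will be recorded in triplicate and separated by at least 1 minute for each replicate". It adds: "Actual time of the assessment must be recorded for each iteration". Footnote n of the protocol's schedule of procedures repeats the spacing.

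**Protocol 8.6.6 (Electrocardiogram Data)** uses a different trigger. Where several values exist for one nominal time point, with a triplicate reading given as the example, "the average of the readings taken for ECG parameters will be used in the data analysis, including the outlier analysis stated below".

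**Elsewhere in the SAP:**
- Section 9.6 plans summaries of observed ECG values, changes from baseline and threshold categories. Its visible text has no averaging rule.
- Table 3 defines the ECG windows in days.
- Section 11.2 lists three changes to protocol-specified analyses. None concerns ECG averaging.

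**The concern.** The step that mentions triplicates is guarded by a condition that correctly collected triplicates do not meet. A programmer who follows the condition keeps one replicate. A programmer who follows the parenthesis takes the mean. Both can say they followed SAP 6.5.1, and they would produce different QTcF, PR, QRS and heart-rate datasets.

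If the condition is followed, the analysis departs from protocol 8.6.6 without the departure being declared. A single reading carries more measurement noise than a mean of three, at baseline and after it. Changes from baseline become more variable, and more subjects cross a category boundary by chance. Resting ECGs are a listed safety endpoint, safety is one of the two primary objectives, and increased heart rate is named in protocol 1.4 as an important potential risk.

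**Working it through.** The plan states no figure on this point, so there is none to reproduce. The check has two parts.

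**1. Applying the rule as written.** Take an illustrative QTcF triplicate of 440, 446 and 455 msec (assumed values). The protocol mean is (440 + 446 + 455)/3 = 447 msec.

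| Gap between replicates | SAP 6.5.1, nominal time in days | SAP 6.5.1, nominal clock time set at the first replicate | Protocol 8.6.6 |
|---|---|---|---|
| 0 min | 447 (mean of 3) | 447 (mean of 3) | 447 |
| 1, 2 or 5 min | 455 (last only) | 440 (first only, being closest) | 447 |

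With day-based windows, three replicates from one session are equally far from the nominal day, so step 2 applies and the later record is kept. With a clock-time nominal point, step 1 already picks one. The mean appears only at a gap of zero, which the protocol's 1-minute spacing rules out. If averaging is triggered by the shared nominal time point, the result is 447 at every gap.

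**2. Size if single replicates were used.** The documents give no QTcF variance, so both SDs are assumptions: between-visit SD *b* and within-session replicate SD *w*.

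- SD of change, single readings: √[2(*b*² + *w*²)]
- SD of change, means of three: √[2(*b*² + *w*²/3)]

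With *b* = *w* = 8 msec:
- Single: √[2(64 + 64)] = √256 = 16.0 msec
- Mean of three: √[2(64 + 21.33)] = √170.67 = 13.1 msec
- Variance ratio: 256/170.67 = 1.5
- P(change > 30) with no drug effect, normal distribution: 1 − Φ(30/16.0) = 3.0% for single readings and 1 − Φ(30/13.06) = 1.1% for means
- In 154 randomized subjects at one post-baseline visit: 154 × 0.0304 ≈ 4.7 against 154 × 0.0108 ≈ 1.7 chance crossings
- P(change > 60), single: 1 − Φ(60/16.0) ≈ 0.009%, or about 0.01 subjects in 154

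With *b* and *w* each taken from 6, 8 and 10 msec:
- The variance ratio runs from 1.2 (*b* = 10, *w* = 6) to 2.0 (*b* = 6, *w* = 10).
- Chance crossings of 30 msec are 1.5 times (*b* = 10, *w* = 6) to 6.7 times (*b* = 6, *w* = 8) as frequent with single readings.
- P(change > 60) from single readings is at most 0.135% (*b* = *w* = 10).

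**The case against.** The best defence is that the SAP plainly intends to average. It names triplicates as the usual case, ECG is the only triplicate in the documents, and the rule is introduced as a general one. Protocol 8.1 says changes to the planned analyses will be described in the SAP, and SAP 11.2 describes none for ECG averaging, so the protocol's mean was not knowingly withdrawn. The later-record step also speaks of two records and the averaging step of two or more, which suits a triplicate better. All of this stands as evidence of intent. It does not repair the condition, which compliant replicates still fail.

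A reader might go further than the documents allow in four ways:

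- **That the SAP has settled on the last replicate.** It has not. The parenthesis points to the mean, and the last replicate follows only from a strict sequential reading with nominal time in days.
- **That the averaging step can never be reached.** The protocol requires individual times, but nothing visible shows that the ECG analysis dataset carries them. The notes to Table 3 allow for assessments with only a date.
- **That Table 3 sets the baseline to one replicate by using the last result before first dose.** The same wording serves vital signs, questionnaires and laboratory tests. It identifies the pre-dose time point and does not say how replicates there are combined.
- **That counts above 60 msec are inflated.** On the assumptions above the effect is negligible.

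It is also fair that extra replicate noise would fall on both randomized arms alike, so it favours neither in the comparison.

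**Conclusion.** The point holds as an internal contradiction in SAP 6.5.1 and a conflict with protocol 8.6.6. The operative condition, applied literally, yields one replicate where the protocol requires the mean of three. Nothing visible in SAP 9.6 or 11.2 resolves this.

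Its reach is limited to descriptive safety ECG summaries of QTcF, PR, QRS and heart rate. The exposed parts are mainly the category for QTcF changes above 30 msec and the absolute thresholds. The primary endpoint, the secondary efficacy analyses and the sample size are untouched.

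The size is conditional twice over: on the literal rule being programmed, and on SDs that the documents do not supply. If the programs already average, no result changes and the SAP text is simply brought into line with them.

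**What to change.** Reword the last step of SAP 6.5.1 and move it to the front: replicates from the same visit or nominal time point are averaged first, using all valid replicates whatever their clock times; the closest-then-later hierarchy then chooses among the visit-level means.

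State that the open-label and randomized-withdrawal ECG baselines are each the mean of the last triplicate before the first dose of that period. Repeat in SAP 9.6 that observed values, changes and threshold categories are all derived from these means, in line with protocol 8.6.6.

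The cost is a sentence or two of SAP text and one derivation step. No new data are needed.
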